5.2 Summary of findings from clinical studies

Two systematic reviews are available on the treatment of complete UCL ruptures. [8,9] Both studies investigated nonoperative and operative treatment of patients with an acute complete tear of the UCL and concluded that no studies directly comparing nonoperative treatment with operative treatment were present. Regarding the current evidence, nonoperative treatment of complete UCL ruptures, including Stener Lesions, has been shown to be effective in most patients. [2,3] Although the ligament sometimes heals with slight laxity, there is no evidence for any benefits to surgery that outweigh the risks of nonoperative treatment.

Pichora et al observed 32 patients with a complete tear, with and without Stener Lesions, treated with bracing for 1 year. [2] Final laxity measured 2.3° on average; 91% of patients either felt normal or had minimal disability. Functional outcomes such as motion, timed dexterity, and grip and pinch strength measured 89% to 99% of the uninjured side. Three patients required secondary surgery. Landsman et al reported 6 out of 40 patients treated nonoperatively (15%) requested surgery, although they included several bony avulsions. [3]

The proposed intervention for complete UCL ruptures, including Stener Lesions, is a trial of cast immobilization with repeat examination after 2 weeks. There is no evidence that suggests that such a delay negatively affects the outcome if surgery is needed. Thumb immobilization of a complete tear is well described and frequently a successful method of treatment. However, qualitative, focused studies comparing cast immobilization with operative treatment are lacking.

V7 01-02-2024 17 of 30

6. METHODS

6.1.1

6.1 Study parameters/endpoints

Main study parameter/endpoint

The Michigan Hand Questionnaire (MHQ), expressed as total MHQ score at 6 months (from date of injury to 6 months after) is the primary endpoint of the study. The MHQ is a validated tool for assessment of functional outcome in patients with pathology of the hand. The MHQ is a questionnaire divided in six subscales; overall hand function, activities of daily living (ADLs), pain, work performance, aesthetics and patient satisfaction with hand function. Each subscale has a formula to calculate a score. The final score is a summation of the six individual item-scores divided by six and goes from 0 (severe disability) to 100 (no disability). [10]

6.1.2 Secondary study

parameters/endpoints

PATIENT REPORTED OUTCOME (PROM)

Since UCL injuries occur to patients of all ages, the expert panel advised to develop multiple communication channels for providing information and obtaining treatment data. Patients will have the choice to fill in the questionnaires between postal mail and online.

Besides the primary endpoint at 6 months from date of injury, the MHQ will be assessed at randomization, at 4 weeks of immobilization (when the immobilizing cast is replaced by a removable cast) and at 3 and 12 months from date of injury.

Patient-Specific Functional Scale (PSFS) is a self-reported, patient-specific outcome measure, designed to assess functional change, primarily in patients presenting with musculoskeletal disorders. Patients are asked to identify up to five important activities they are unable to perform or are having difficulty with as a result of their problem i.e. putting socks on. In addition to identifying the activities, patients are asked to rate, on an 11-point scale, the current level of difficulty associated with each activity. Following the intervention, patients are asked again to rate the activities previously identified and are given the chance to nominate new problematic activities that might have arisen during that time. "0" represents unable to perform, "10" represents able to perform. Patients select a value that best describes their current level of ability on each activity assessed. The PSFS will be assessed at randomization, after 4 weeks of immobilization (when the immobilizing cast is replaced by a removable cast) and at 3, 6 and 12 months from date of injury.

EQ-5D-5L is a measure of health-related quality of life that can be used in a wide range of health conditions and treatments. The EQ-5D consists of a descriptive system and the EQ VAS. The descriptive system comprises five dimensions: mobility, self-care, usual activities, pain/discomfort and anxiety/depression. The EQ VAS records the patient's self-rated health on a vertical visual analogue scale. This can be used as a quantitative measure of health outcome that reflects the patient's own judgment. The score on the five dimensions can be presented as a health profile or can be converted into a utility score based on an available Dutch scoring algorithm (www.euroqol.org). The area under the curve of utility scores over time will be used to express the effect on quality of life in

V7 01-02-2024 18 of 30

QALY's. The EQ-5D-5L will be assessed at randomization and 2, 3, 6 and 12 months from date of injury.

The Numeric Pain Rating Scale (NPRS) will be used to assess pain, where 0 implies no pain and 10 the worst possible pain measured at randomization, after 4 weeks of immobilization (when the immobilizing cast is replaced by a removable cast) and at 3, 6 and 12 months after date of injury.

Patient satisfaction will be measured by using the ICHOM Satisfaction with treatment results questionnaire (self designed by ICHOM) measured at randomization, after 4 weeks of immobilization (when the immobilizing cast is replaced by a removable cast) and at 3, 6 and 12 months after date of injury.

The adapted Dutch institute for Medical Technology Assessment (iMTA) Medical Consumption Questionnaire (iMCQ) and iMTA Productivity Cost Questionnaire (iPCQ) will be used to measure the amount of medical consumption, sick leave from work or lost productivity while at work and out-of pocket expenses due to a complete tear of the UCL and the questionnaires are adjusted for this study. A shortened version of the iPCQ including only questions about sick leave from work and lost productivity while at work is measured at baseline (at randomization). The full iMCQ and iPCQ will be measured at 2 (over the last 2 months), 3 (over the last month), 6 (over the last month, this will be multiplied by 3 for the cost effectiveness analysis), and 12 months (over the last month, this will be multiplied by 6 for the cost effectiveness analysis)) after injury. Data will also be cross-verified with data from the Electronic Patient Record (EPD). If the data appears distorted, the analysis will be conducted using various scenarios to ensure its accuracy.

CLINICIAN REPORTED OUTCOME MEASURES (CROM)

Functional outcomes will be assessed by the head investigator of the study site to improve the reliability of measurements as much as possible. Before and during the study, multiple meetings will be scheduled with local investigators to optimize study logistics. All measurements will be performed as described in the International Consortium for Health Outcomes Measurement International (ICHOM) standard outcome set for hand and wrist conditions. [11]

Range of motion (ROM): flexion and extension of the metacarpophalangeal (MCP) joint and interphalangeal joint (IP) and palmar abduction of the carpometacarpal (CMC) joint are measured with a goniometer. The first measurement is performed at both sides. ROM is measured from the moment the patient is allowed to move the MCP joint; after 4 weeks of immobilization (when the immobilizing cast is replaced by a removable cast) and at 3, 6, and 12 months.

Kapandji-score is used for assessing the opposition of the CMC joint. The opposition test consists of touching the four long fingers with the tip of the thumb. The more the tip of the thumb is able to oppose to the base of the pink, the higher the score will be. [12] The first measurement is performed at both sides. Kapandji score is measured from the moment the patient is allowed to move the MCP joint after 4 weeks of immobilization (when the immobilizing cast is replaced by a removable cast) and at 3, 6, and 12 months.

V7 01-02-2024 19 of 30

Grip strength: measured with a hand-held dynamometer. The measurement includes three trials of maximum grip force using the second handle of a calibrated dynamometer, with the elbow in 90° flexion. Dynamometer settings will be on setting two for all patients. Each center will use the same type of dynamometer. The mean score of three trials will be used for analysis as an absolute measure. Grip strength is measured at 3, 6, and 12 months. The first measurement is performed at both sides.

Pinch strength: key pinch/lateral pinch and tip pinch will be measured. Key pinch includes three trials of maximum force between the radial side of the index finger and the pulp of the thumb, using a calibrated pinch gauge, with the elbow in 90° flexion. Tip pinch includes three trials of maximum force between the tip of the index finger and the tip of the thumb, using a calibrated pinch gauge, with the elbow in 90° flexion. Each center will use the same type of pinch gauge. The mean score of three trials will be used for analysis as an absolute measure. Pinch strength is measured at 3, 6, and 12 months. The first measurement is performed at both sides.

COMPLICATIONS

- Conservative treatment: pressure ulcers, neuropraxia or injury to the sensory superficial branches of radial nerve, arthrosis, chronic instability or limited function.
- Perioperative: vascular damage, nerve or tendon laceration.
- Postoperative: surgical site infection, repeat operation, pressure ulcers, neuropraxia or injury to the sensory superficial branches of radial nerve, arthrosis, chronic instability or limited function.

Peri- and postoperative complications will be recorded according to tthe Clavien-Dindo Classification for hand surgery. Repeat operation and subsequent description of the additional treatment method will be reported.

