5. TREATMENT OF SUBJECTS

5.1 Investigational treatment

INTERVENTION

Patients in the intervention group receive non-operative treatment of the thumb using a cast to immobilize the metacarpophalangeal (MCP) and carpometacarpal (CMC) joint of the thumb in a neutral position for 4 weeks, followed by a removable cast for 4 weeks. During this time frame, the ruptured UCL ligament has a chance to heal. After 4 weeks of immobilization, all patients will be referred for hand therapy. The exact details of the treatment, from first presentation to full recovery, are described step-by-step.

1) First presentation at the ED (pre-treatment protocol)

This pre-treatment protocol applies to patients who present at the ED with a sustained trauma to the thumb, resulting in acute pain and swelling around the MCP joint of the thumb. These patients are potentially eligible for inclusion in the study and receive a temporary cast to immobilize the MCP and CMC joint of the thumb. An appointment with the surgeon is scheduled within 3-5 days from presentation at the ED.

2) First presentation at the outpatient clinic (start intervention)

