- When the hand surgeon concludes that there is a firm endpoint (meaning adequate healing of the UCL ligament) cast immobilization is continued for another 2 weeks, until a total immobilization period of 4 weeks is completed. An appointment is scheduled after 4 weeks of cast immobilization.
- When there is no firm endpoint of the UCL or there is doubt about a firm endpoint, patients are scheduled for surgery within 5 working days (switching to usual care; see description usual care).

4) Outpatient clinic visit after 4 weeks of immobilization

The patient visits the hand surgeon. The immobilization cast is removed and replaced for a removable cast, which allows the patient to start exercising. Patients are instructed to start using the thumb for regular daily activities, without putting pressure on it, and start thumb exercises consisting of a combination of opposition and abduction/adduction movements. Patients are advised to repeat the exercises 5-10 times a day. A referral is made to the hand therapist to guide this process. Hand therapy will start within 1 week. The frequency and duration of hand therapy will be determined by the hand therapist. Hand therapists from all hospitals will collaborate to achieve consensus on a treatment protocol. Outcome measures are evaluated in the form of physical examination and surveys. A new appointment is scheduled at 3 months.

- 5) Visit to outpatient clinic at 3 months (standard visit)
 Progression of treatment is evaluated with the patient and expectations are managed.
 Outcome measures are evaluated in the form of physical examination and surveys. A new appointment is scheduled at 6 months.
- 6) Visit to outpatient clinic at 6 months (standard visit)
 Progression of treatment is evaluated with the patient and expectations are managed
 Outcome measures are evaluated in the form of physical examination and surveys. A
 new appointment is scheduled at 12 months.
- 7) Visit to outpatient clinic at 12 months (visit for study purpose)

 Treatment outcome is evaluated for study purposes. Outcome measures are evaluated in the form of physical examination and surveys.

USUAL CARE/COMPARISON

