- If the UCL is ruptured in the middle of the ligament, sutures are used to reattach the ligament remnants together.
- When no viable UCL ligaments are present, the UCL is reattached directly to the bone using suture anchors.

Patients can choose between regional anesthetics of the upper arm or complete sedation. The procedure normally takes 30-45 minutes. Postoperatively, patients are treated with a cast immobilizing the CMC and MCP joint for 4 weeks followed by a removable cast for 4 weeks. After 10 days the skin sutures are removed at the outpatient clinic and the cast is renewed. [7]

4) Outpatient clinic visit 4 weeks after surgery
This part of the treatment protocol is identical to the protocol of the intervention group.

5) Visit to outpatient clinic at 3 months (standard visit)
This part of the treatment protocol is identical to the protocol of the intervention group.

6) Visit to outpatient clinic at 6 months (standard visit)

This part of the treatment protocol is identical to the protocol of the intervention group.

7) Visit to outpatient clinic at 12 months (visit for study purpose)
This part of the treatment protocol is identical to the protocol of the intervention group.

V7 01-02-2024 16 of 30

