If the null hypothesis in this study of nonoperative treatment not being clinically non-inferior at six months is not rejected, but indeed lower costs are associated with nonoperative treatment, then incremental cost-effectiveness ratios will be calculated as the extra savings per extra unit in MHQ score lost or the extra savings per additional QALY lost. If the null hypothesis is rejected, a costs analysis and an outcome analysis will be done as distinct partial economic evaluations. The time horizon will be 12 months. It is expected that effects and costs beyond 12 months are similar for both treatment strategies and that a lifetime time horizon is redundant.

Differences between groups will be assessed after correction for bias and using accelerate non-parametric bootstrapping to account for sampling variability, generating 5,000 replications. Results will be presented graphically by cost-effectiveness planes. Cost-effectiveness acceptability curves will be drawn for various levels of willingness-to-pay per QALY up to €50,000, because higher levels cannot be justified by the maximum observable disease burden in this target group of patients. A scenario analysis will be applied by excluding the productivity losses following sick leave. Subgroup analyses will be performed for patients with a paid job.

Missing cost and effect data will be imputed using multiple imputation according to the MICE algorithm developed by van Buuren. Rubin's rules will be used to pool the results from the different multiply imputed databases. [14]

Measurement and valuation of costs

We will gather data on the use of resources and the related costs regarding health care (e.g. medical specialist, hand-physiotherapist, treatment of complications), productivity losses (absenteeism (sick leave) and presenteeism (lowered efficiency while at work due to sick leave from work and lowered productivity while a work)) and out-of-pocket

V7 01-02-2024 25 of 30

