expenses by patient and family members (e.g. health related travel, extra private help). The Dutch iMTA Medical Consumption Questionnaire and iMTA Productivity Cost Questionnaire will be adapted to and prepared for the current study setting and disseminated to patients for completion after two, three, six and twelve months of follow up.(11,12) Case report forms or electronic patient dossiers will be used to gather inhospital data. Unit costing will be based on the most recent Dutch guideline on costing in health care research at the time of data analysis. Costing of productivity losses will adhere to the friction costs approach with the current friction period at time of analysis.(13) The base year for costing will be 2022, with unit costs price-indexed if originating from other calendar years.

Patient outcome analysis

Patient outcome analysis in addition to the clinical outcome measures relevant to patients (disability, pain, hand function) the economic evaluation will include the measurement of health status at baseline (within 2 weeks after trauma), at two, three, six and 12 months after injury with the EQ-5D-5L. [15] This questionnaire consists of 5 items, measuring (at 5-point scales) whether patients experience problems, and if so, to what extent with regard to mobility, self-care, daily activities, pain/complaints, and mood. Existing health valuation scoring algorithms (Dutch reference values available through www.euroqol.org) will be used to assign a health utility to each 5-items score pattern. The number of QALYs for each patient will subsequently be calculated by interpolation between successive measurement and determining the area under the curve for the follow-up period of 12 months.

V7 01-02-2024 26 of 30

ETHICAL CONSIDERATIONS

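### EQ-5D-5L is not measured between randomisation and 2 months, so one straight line of about 56 days spans surgery and most of the rigid-cast phase, and the early QALY difference may be under- or overstated

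*Protocol*

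**What the plan says.** - **EQ-5D-5L schedule.** Section 6.1.2: "The EQ-5D-5L will be assessed at randomization and 2, 3, 6 and 12 months from date of injury". The patient outcome part of the cost-effectiveness section gives the same points: "at baseline (within 2 weeks after trauma), at two, three, six and 12 months after injury with the EQ-5D-5L". The readable part of Figure 2 (section 6.3) shows MHQ and PSFS, but no EQ-5D, at the removable-cast visit.
- **QALY method.** "The number of QALYs for each patient will subsequently be calculated by interpolation between successive measurement and determining the area under the curve". On the horizon: "The time horizon will be 12 months".
- **Surgical arm (section 5.1).** "An appointment with the surgeon is scheduled within 3-5 days from presentation at the ED". Baseline surveys are taken at that clinic stage, before the operation. Surgery follows within 5 working days of the visit. Afterwards "patients are treated with a cast immobilizing the CMC and MCP joint for 4 weeks followed by a removable cast for 4 weeks".
- **Cast arm (section 5.1).** Four weeks of rigid cast that include the time since the ED, then four weeks of removable cast. If there is no firm endpoint at the two-week re-examination, or doubt about it, "patients are scheduled for surgery within 5 working days (switching to usual care; see description usual care").
- **Other instruments (section 6.1.2).** MHQ, PSFS, pain and satisfaction are collected when the rigid cast comes off. The 2-month cost questionnaires look back over the first two months.

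**The concern.** The two strategies differ mainly by an operation and by how long the rigid cast stays on. Both differences arise in the first weeks, and the instrument that produces the QALYs is silent in those weeks. It is measured once before surgery and next when most patients are in the removable cast or just out of it. The area between is whatever a straight line gives, so a dip and recovery inside the interval leaves no trace.

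Costs and effects are also treated unequally. Early resource use and sick leave enter through the 2-month look-back, while the health loss of the same weeks is not measured. Cost per QALY is the primary outcome of the cost-utility analysis, and acceptability curves are planned up to EUR 50,000 per QALY, so small utility differences carry weight there.

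This is a data-collection matter. Multiple imputation can fill in a scheduled value that is missing. It cannot supply a time point that was never scheduled.

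**Working it through.** The protocol states no utility or QALY figure, so there is none to reproduce. The check is a day count on the protocol's own schedule, followed by an illustration with assumed utilities.

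**1. Day count, ED visit on the day of injury.** Five working days are taken as up to 7 calendar days, and 2 months as 2 × 365.25/12 = 60.9 days.

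| Event | Surgical arm | Cast arm |
|---|---|---|
| Baseline EQ-5D | day 3–5 | day 3–5 |
| Surgery | by day 10–12 | conversions by 14 + 7 = day 21 |
| Rigid cast ends | by day 38–40 | day 28 (converters by 21 + 28 = day 49) |
| Removable cast ends | by day 66–68 | day 28 + 28 = 56 |
| Next EQ-5D | day 61 | day 61 |

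With baseline on day 5 the gap is 60.9 − 5 = 55.9 days, and 55.9/365.25 = 15% of the horizon.

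**2. Late presenters.** Section 4.3 admits ED presentation up to 13 days after injury. Baseline is then day 16–18, surgery by day 23–25, and the surgical rigid cast ends by day 51–53. A converter's rigid cast can run to 13 + 49 = day 62, just past the 2-month point. The gap is shorter (60.9 − 18 = 42.9 days) but still contains the operation.

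**3. What the line cannot see.** Assume that surgery lowers utility by d, fading linearly to zero over T days, with no lasting difference at 2 months. The loss per operated patient is d × T / 2 / 365.25. Conversions, about 1 in 10 of the cast arm by the protocol's expectation, are assumed to incur the same loss, so the between-arm difference is 0.9 times that.

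| d | T (days) | Loss per operated patient | Recorded as planned | Net between arms | At EUR 50,000 per QALY |
|---|---|---|---|---|---|
| 0.1 | 14 | 0.0019 | 0 | 0.0017 | EUR 86 |
| 0.2 | 14 | 0.0038 | 0 | 0.0034 | EUR 172 |
| 0.2 | 28 | 0.0077 | 0 | 0.0069 | EUR 345 |
| 0.3 | 28 | 0.0115 | 0 | 0.0103 | EUR 517 |

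**4. What the line can add.** On day 61 a cast-arm patient is out of the removable cast (day 56), while a surgical patient may wear it to day 68. If this produces a utility gap g at 2 months, the first interval credits the cast arm with g × 55.9 / 2 / 365.25 = 0.0765 × g. With an assumed g = 0.05 that is 0.0038 QALY, or EUR 191. A gap of 0.0017/0.0765 = 0.02 puts in as much as the smallest unseen loss takes out. For the largest unseen loss the figure is 0.0103/0.0765 = 0.13. The two effects are of the same order and opposite sign.

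**5. Does an added point help?** Take baseline day 5, surgery day 12, and extra points on day 19 (2 weeks after randomisation) and day 40 (rigid cast off). The four losses of step 3 are then estimated at 0.0024, 0.0048, 0.0072 and 0.0108, against true values of 0.0019, 0.0038, 0.0077 and 0.0115. With the day-40 point alone the estimate is 0 in all four cases, because the assumed loss has resolved by then.

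**The case against.** The best answer is that the schedule is stated twice without contradiction, the interval is interpolated rather than dropped, and early function and pain are recorded by other instruments. The primary endpoint is untouched. So is the cost per unit of hand function, which is the other half of the economic evaluation. If non-inferiority is shown, costs and outcomes are to be analysed separately, and the incremental ratio belongs to the other branch. All of this stands and limits the reach of the point. It does not remove it, since a separate QALY outcome would carry the same gap.

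Three stronger readings are tempting, and the protocol supports none of them.

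- **That the analysis is biased against the cast strategy.** An unseen post-operative loss would act that way, but the longer removable-cast period after surgery can act the other way at the 2-month point. Which prevails depends on utilities that the protocol does not give.
- **That the missed part is most of the true QALY difference.** The cost-effectiveness section expects similar effects only beyond 12 months. It does not say that the arms are equal between 2 and 12 months, where three of the remaining EQ-5D measurements (3, 6 and 12 months) fall.
- **That everything separating the arms is hidden.** Only departures from the straight line are lost. The removable-cast phase can extend past 2 months, and so can a late converter's rigid cast.

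**Conclusion.** The point holds as a weakness in data collection for the secondary cost-utility analysis. One straight line of about 56 days (15% of the horizon) bridges the operation, early wound recovery, conversions decided at two weeks, and the between-arm difference in rigid-cast duration. The early QALY difference may be under- or overstated, and the direction is not established.

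The unseen post-operative part is about 0.002 to 0.010 QALY per patient, or EUR 86 to 517 at EUR 50,000 per QALY. This rests on assumed losses of 0.1 to 0.3, linear fading over 14 to 28 days, 10% conversions with the same loss, and equal utility at baseline and 2 months. The day count rests on the protocol alone. The change is worth making because it is cheap and the information cannot be recovered later. The non-inferiority conclusion does not depend on it.

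**What to change.** 1. Add the EQ-5D-5L to the questionnaire pack already completed when the rigid cast is replaced by the removable one.
2. Add one online or postal EQ-5D-5L at the same fixed interval after randomisation in both arms, about 2 weeks. Tying it to randomisation keeps it after the scheduled primary surgery in late presenters too. Three weeks from injury would not, since their surgery can fall on day 23–25.
3. Enter both in the area under the curve at their actual dates, because the removable-cast visit falls at different times from injury in the two arms. Update section 6.1.2, Figure 2 and the patient outcome text together.

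**Cost.** One extra short form, and one more form in an existing pack. Online and postal completion are already offered. Late conversions are captured only in part: for a patient seen on the day of injury the 2-week form falls on day 17–19, while conversion surgery can be as late as day 21. Patients already past these times have only the existing points. Use those for them, and report a sensitivity analysis that applies the existing points to everyone.
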